Children requiring prolonged courses of PN are at risk for developing PN associated liver disease. We hypothesize that although omega-6 fatty acid emulsions prevent fatty acid deficiency, they are not cleared in a manner similar to enteral chylomicrons and therefore accumulate in the liver and resulting in steatotic liver injury. We further hypothesize that a fat emulsion comprised of omega-3 fatty acids (i.e., fish oil) such as Omegaven® would be beneficial in the management of steatotic liver injury by its inhibition of de novo lipogenesis, the reduction of arachidonic acid-derived inflammatory mediators, prevention of essential fatty acid deficiency through the presence of small amounts of arachidonic acid, and improved clearance of lipids from the serum. Animal studies have shown that IV fat emulsions (IFE) such as fish oil that are high in eicosapentaenoic and docosahexaenoic acid reduce impairment of bile flow which is seen in cholestasis caused by conventional fat emulsions. Furthermore, we hypothesize that that intravenous omega three fatty acids will be well tolerated and might reduce the inflammatory effect in the liver of prolonged PN exposure and could potentially reverse any hepatic dysfunction due to PN/IFE use. By administering Omegaven® in place of conventional phytosterol/soybean fat emulsions we may reverse or prevent the progression of PN associated cholestasis and thus allow the patient to be maintained on adequate PN until they are able to ingest adequate nutrition enterally.

1. Specific Aims /Objectives

1. To determine the safety profile of an intravenous omega-3 fat emulsion (Omegaven®)

Hypothesis for Aim 1:

1.1 – After starting Omegaven® on PN, the rate of fatty acid deficiencies and imbalances will be as low as before Omegaven®. Also, the rate of triglyceride events > 400 mg/dL with Omegaven® will be similar to that seen with PN administered with soy oil IFE (conventional emulsion, i.e., Intralipid®).

1.2 – PN containing Omegaven® will be safe for patients with respect to the risk of unexpected bleeding, coagulopathies, and other adverse events.

1.3 – PN containing Omegaven® will promote more short-term growth and development than conventional fat emulsions.

2. To determine if established PN associated liver disease can be reversed or its progression halted by using a parenteral fat emulsion prepared from fish oil as measured by normalization of serum levels of hepatic enzymes and bilirubin.

Hypothesis for Aim 2:

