Assessment of the effect of treatment will be based on a non-randomized, open-labeled, prospective study of intravenously administered Omegaven[®] fat emulsion to determine safety and preliminary efficacy in the treatment of PN associated liver injury. This treatment group will be compared to a group based on historical controls, i.e., a subset of patients (those whose direct bilirubin levels was ever > 2 mg/dL) previously studied by Andorsky et al.(31) This study included neonates treated between 1986 and 1996 who depended on parenteral nutrition for at least 90 days after surgical therapy for congenital or acquired intestinal diseases. Our study will primarily follow the patients included in Andorsky et al. study from 2 months before direct bilirubin first reached a level > 2 mg/dL (baseline date) until 2 months after patients either reached 3 consecutive bilirubin levels \leq 2 mg/dL or reached one bilirubin level \leq 2 mg/dL and were weaned from PN died, or underwent a liver transplant. In our exploratory analyses, we will include the entire available follow-up time in Andorsky et al. dataset for each patient.

b. Patient Selection and Inclusion/Exclusion Criteria

Omega-3 Fat Emulsion (Omegaven[®])

After the diagnosis of PNALD is made, patients who are followed by the Clinical Nutrition Service (CNS) or General Surgery Program, in conjunction with the patient's primary physician, will contact [name] or [name] and an evaluation will be performed. Cases may also include referrals of patients with PNALD from other healthcare facilities or self-referrals. If the patient's parents or guardians agree to participate in the study, informed consent will be obtained. The history of present illness and past medical history will be reviewed with the guardian and pertinent demographic and medical information will be recorded on data collection forms. This form will be used to record all laboratory results, nutritional history, and descriptions of any liver biopsies performed.

Though most patients receiving parenteral nutrition do not develop end stage liver disease, there is a small percentage of patients, typically infants and children on prolonged courses of parenteral nutrition, who do go on to develop fulminate liver failure. The study population of this protocol is limited to patients felt to fulfill any one of the following conditions:

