Because both Intralipid® and Liposyn® II are isotonic, both could be infused through either a central or peripheral line. Both products are compatible with parenteral nutrition solutions and were co-infused via y-site. Source container hang times varied during this period, and IFE was either infused from a single container over 24 hours or the container was changed every 12 hours per CDC recommendations. Also during this period, the administration method of PN changed. Prior to 1999, standard 0.2 micron inline filters were used routinely and only PN but not IFE could be infused through them (IFE was infused via y-site beneath the filter). After 1999, 1.2 micron filters became the standard inline filter, allowing for IFE to be filtered along with the PN solution.

Duration of Therapy

Patients remained on either Liposyn® II or Intralipid® until weaned from PN.

Discontinuation of Therapy

Patients at risk for malnutrition or resumption of PN were typically followed by the Clinical Nutrition Service for several months following discontinuation of PN.

ADDITIONAL PREDICTORS OF INTEREST

Since decisions about starting Omegaven® administration will follow a compassionate protocol, we expect that patients receiving Omegaven® will present more severe liver disease than the controls from the historical cohort. Therefore, to correct confounding biases, we anticipate the need to adjust for potential predictors of liver outcomes at baseline. Baseline will be defined as: the date that treatment starts for Omegaven® patients and on the date that patient reached bilirubin levels > 2 for soybean based fat emulsion patients.

The following predictors of liver disease will be considered:

- Baseline direct bilirubin levels.
- Diagnosis of Necrotizing Enterocolitis (vs. any other disease)
- Gender (male vs. female)
- Age (≥ 8 months vs. < 8 months)
- Gestational age
- Birth weight
- Race

To assess patients comparability, we will also descriptively explore trends in direct bilirubin level before the beginning of follow-up (start of treatment date for Omegaven® patients and date in which direct bilirubin level raised to > 2 mg/dL for control patients)

Subgroup Analysis

With exploratory purposes, we will describe safety and/or efficacy of Omegaven® in subgroups of patients including younger (vs. older) patients at baseline, patients who presented with infections (vs. who did not),

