Analysis of Baseline Characteristics

For statistical purposes, baseline values will be defined as the last measurement before starting to administer Omegaven® for patients, in the treatment group, and as the measurement taken when a patient first had a direct bilirubin level > 2 mg/dL recorded, in the historical control group. Descriptive statistics for all baseline relevant risk factors will be summarized for Omegaven® (omega-3 based fat emulsion) and historical control (soybean oil fat emulsion) groups. Associations between categorical predictors and Omegaven® vs. soybean oil fat emulsion groups will be tested through chi-square tests. Associations between continuous predictors and treatment groups will be studied through means (and standard deviations) and t-tests, or medians (and interquartile ranges) and Wilcoxon tests, when appropriate.

Analysis of Safety and Tolerability of Omegaven®

All primary safety and tolerability analyses will be based on descriptive statistics. In secondary analyses, we will also assess the statistical significance of differences. Some safety and tolerability outcomes will be measured only in the Omegaven® group. For those, we will compare results before starting PN with Omegaven® (while receiving PN with soybean oil fat emulsions) with after starting PN with Omegaven®. The period receiving Omegaven® will start to be counted 30 days after beginning PN with Omegaven® for the main analysis. Outcomes measured in the Omegaven® and soybean oil fat emulsion groups will be described separately for each of those groups for a period starting 30 days after baseline, i.e., 30 days after starting PN with Omegaven®, for the treatment group, and 30 days after bilirubin > 2 mg/dL, for the soybean oil fat emulsion group.

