We will also compare nutritional outcomes of the two groups including difference in weight-for- age Z-scores and height-for-age Z-scores from baseline to the moment in which the child starts enteral feeding and to the moment in which the child receives less than 10% of their calories from PN. Comparison between study groups will be performed via t-test or Wilcoxon tests, as appropriate. Using linear regression, we will explore adjustment for baseline alternative predictors of interest. Trends over time in Z-scores will also be explored using regression with repeated measure methods.

Analysis of Efficacy of Omegaven®

The primary outcome to gain preliminary evidence of efficacy will be based on the time from baseline to normalization of bilirubin level, i.e, first time point among three consecutive in which bilirubin is < 2 mg/dL. We do not anticipate that any subject will present a rebound on direct bilirubin after normalization. However, we will describe the cohort with respect to the frequency of rebounds in bilirubin levels.

Crude comparisons of time to normalize direct bilirubin levels between Omegaven® and soybean oil fat emulsion patients will be based on Kaplan-Meier curves and log-rank tests. We will estimate hazard ratios and adjust for potential baseline confounders using Cox-proportional hazard models. For all survival analysis based on non-parametric or semi-parametric methods, we will attribute an infinite time to event (i.e., time to event larger than the largest follow-up time in the whole study population) for subjects who die or receive a liver transplant before bilirubin is normalized. Subjects who die before their bilirubin levels normalize (particularly due to liver failure) have in fact the worse outcome (infinite time to normalize bilirubin) and were not censored before reaching the endpoint of interest. Results of these analysis will be compared with results of analysis excluding subjects who die or are transplanted. Time to reach a total bilirubin of 1.2 will also be compared using survival analysis methods. Analysis of this outcome will proceed as described for direct bilirubin.

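### The growth comparison never names baseline Z-score as a covariate, so the raw change difference can shift, in an unknown direction, if the two non-randomised groups start at different Z-scores

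*Combined protocol and SAP*

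**What the plan says.** Hypothesis 1.3 (section 1, Specific Aims) is a superiority statement: "PN containing Omegaven® will promote more short-term growth and development than conventional fat emulsions".

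The nutritional paragraph of Analysis of Safety and Tolerability (section 5c) sets the outcome as the "difference in weight-for- age Z-scores and height-for-age Z-scores from baseline to the moment in which the child starts enteral feeding", with a second end point at the time PN supplies under a tenth of calories. The only between-group test it names is: "Comparison between study groups will be performed via t-test or Wilcoxon tests, as appropriate". Two exploratory analyses follow: "Using linear regression, we will explore adjustment for baseline alternative predictors of interest" and "Trends over time in Z-scores will also be explored using regression with repeated measure methods".

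The covariates are listed under Additional Predictors of Interest, introduced by "The following predictors of liver disease will be considered". They are direct bilirubin, necrotizing enterocolitis, gender, age, gestational age, birth weight and race. Baseline weight- or height-for-age Z-score is not among them and is not named as a covariate anywhere else.

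On design, the plan states: "Assessment of the effect of treatment will be based on a non-randomized, open-labeled, prospective study". The comparison is with historical controls. Baseline is the start of treatment for Omegaven patients and the first direct bilirubin above 2 mg/dL for controls (Analysis of Baseline Characteristics).

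On the status of testing, the safety section states: "All primary safety and tolerability analyses will be based on descriptive statistics". Significance tests are secondary, and section 5d gives no power or sample size for growth.

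**The concern.** A change score usually correlates negatively with its own starting value. In a randomised trial the starting values balance on average, so this costs only precision. Here they need not balance. Allocation is not random, and the two arms enter follow-up at different clinical moments. The original control cohort was diagnosed with short bowel syndrome as neonates, while the Omegaven criteria set no age limit. A difference in starting Z-score is therefore plausible.

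If one exists, part of the difference in Z-score change between groups could reflect where each group began and not which emulsion it received. This would affect the estimate itself, whether or not a p-value is attached. Potential Study Limitations argues that severity differences would only dilute the apparent benefit of Omegaven. For a change score that argument is not secure, because the shift can go either way depending on which group starts lower. The efficacy side already lists the baseline value of its own marker, direct bilirubin. Growth has no equivalent term.

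**Working it through.** **Inputs from the documents.** Outcome: change in Z-score from baseline. Named test: unadjusted t-test or Wilcoxon. Allocation: non-randomised. Covariate list: seven items, no baseline Z-score. Group sizes of 20, 25 and 30 appear only in the power tables for adverse events. The plan has no figure for growth to reproduce.

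**Inputs assumed.** Baseline-to-follow-up correlation rho from 0.3 to 0.9, equal variance at both times, and a common follow-up interval. None is stated in the documents. The last is a simplification, because the growth interval ends at patient-specific feeding milestones.

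**Step 1: shift in the raw change, common mean.** With no treatment effect and both groups regressing to the same mean M, a group starting at b has expected follow-up M + rho(b - M). Its expected change is (1 - rho)(M - b). For groups starting at b1 and b2, the difference in change is (1 - rho)(b2 - b1), in favour of whichever starts lower. For a 1.0 Z gap at rho 0.5 this is 0.5 x 1.0 = 0.5 Z; at rho 0.8 it is 0.2 x 1.0 = 0.2 Z.

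**Step 2: the opposite case.** Suppose each group stays around its own mean. Expected change is zero in both, so the raw comparison is unbiased. The baseline-adjusted estimate is the follow-up difference minus rho times the baseline difference: gap - rho x gap = (1 - rho) x gap, in favour of the group that starts higher. The same quantity is now the error of the adjusted analysis. This is Lord's paradox, and it is why both results are needed.

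**Step 3: precision.** The change score has variance 2 sd^2 (1 - rho). ANCOVA has sd^2 (1 - rho^2). The ratio is (1 + rho)/2. With a baseline gap of D SD and equal groups, the ANCOVA variance is multiplied by 1 + D^2/4, which is 1.25 at D = 1.

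| Assumed rho | Shift per 1.0 Z gap (common mean) | Variance ratio ANCOVA/change, no gap | ANCOVA power when change score has 80%, no gap | Variance ratio with 1 SD gap |
|---|---|---|---|---|
| 0.3 | 0.70 Z | 0.65 | 93.5% | 0.81 |
| 0.5 | 0.50 Z | 0.75 | 89.9% | 0.94 |
| 0.7 | 0.30 Z | 0.85 | 86.0% | 1.06 |
| 0.8 | 0.20 Z | 0.90 | 84.0% | 1.13 |
| 0.9 | 0.10 Z | 0.95 | 82.0% | 1.19 |

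Power is by normal approximation, two-sided 0.05. The last column crosses 1 at rho 0.6, since 1.25 x 1.6/2 = 1.00. With a 1 SD gap, a true effect of 0.5 SD and 20 to 30 per group, ANCOVA gains 1.9 to 2.5 points of power at rho 0.5 and loses 1.3 to 5.1 points at rho 0.7 to 0.9.

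**The case against.** The strongest reply is that the plan does not leave the comparison unadjusted. The two sentences after the named test provide for regression adjustment and repeated-measures modelling. The covariate list is headed as predictors of liver disease and is not declared complete for growth. Baseline risk factors are to be compared between groups, and non-comparability is acknowledged as the main limitation. All of this stands. It narrows the gap to one unnamed covariate in an exploratory model, but does not close it: nothing commits the analyst to the starting Z-score, and the only named test ignores it.

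A second reply is that adjustment is not automatically the less biased choice in groups drawn from different populations. Step 2 confirms this. It is a reason to show both analyses, not to omit the adjusted one.

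A third reply is that the consequence is small. The primary safety analyses are descriptive, growth is not among the primary safety outcomes in section 5c, and sample size was not set by power. This also stands and limits the severity.

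A reader might also infer that the change-score test throws away about 10 points of power. The documents do not support that. They give no correlation, SD, effect size or target power for growth. A figure near 10 needs an assumed rho close to 0.5 and equal baselines, which is the opposite of the situation that creates the bias concern.

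**Conclusion.** The point holds as a minor one. The named growth comparison ignores the starting Z-score in groups that may well differ on it, and the planned exploratory regression does not name that covariate. If the groups differ at baseline and regress to a common mean, the raw difference is shifted by (1 - rho) times the gap: 0.5 Z per 1.0 Z at rho 0.5, 0.2 Z at rho 0.8. If each group has its own mean, the raw difference is unshifted and the adjusted estimate moves instead. Intermediate cases fall between these.

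It is tempting to conclude that the bias favours Omegaven because its patients are expected to be sicker. The documents expect more severe liver disease in that group, but report no baseline Z-scores and do not say which group starts smaller. The direction is unknown. No power loss is claimed, for the reasons given under the objection.

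**What to change.** In the nutritional paragraph of section 5c, specify for weight and for height a linear regression of follow-up Z-score on group and baseline Z-score. Add the listed predictors only as far as the sample size allows, since seven of them would be heavy for groups of 20 to 30. Report this estimate beside the raw change comparison. State that the two can differ when the groups have different underlying means, and that Hypothesis 1.3 will be interpreted cautiously if they disagree. Show baseline Z-scores by group in the baseline table.

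The model needs one defined follow-up time. Section e (Definition of Primary and Secondary Outcomes/Endpoints) ends the growth interval at 10% PN or when PN stops, while section 5c uses the start of enteral feeding and a PN share below 10% of calories. These should be reconciled in the same edit.

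The cost is wording only. The baseline Z-score must already exist for the change to be computed. The downside is an extra model term, possible loss of precision if the baseline gap is large and rho is high, and two results to present and reconcile.

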As previously mentioned, Omegaven® may be infused in the same manner as conventional fat emulsions through either a central or peripheral line. The emulsion is isotonic. It is compatible with parenteral nutrition solutions and may be co-infused via y-site. Per Infection Control, source containers must be changed every 12 hours and unused product discarded. Omegaven® may be infused through a 1.2micron inline filter.

Dose Modification

Lipid Intolerance

If lipid intolerance develops, defined as serum triglyceride levels > 200 mg/dL, the following will be considered prior to reducing the dose:

- a) If the level was obtained while the patient was receiving a continuous 24-hour infusion of Omegaven®, the total dose should be infused over 20 hours, and a repeat serum triglyceride level obtained prior to resuming the infusion 4 hours later.

b) Other sources of lipid intolerance should be considered and addressed (drugs, renal disease)

If the triglycerides continue to remain high despite the aforementioned interventions, a dosage reduction of 25% of the current dose will be considered.

High Glucose Infusion Rate

Subjects with a high glucose infusion rate (GIR) will have a dose increase up to 1.5 grams/kg/day to allow for a reduction in PN calories from carbohydrates at the discretion of the Omegaven study team and the nutrition service.

Duration of Therapy

Patients will remain on Omegaven® until weaned from PN. Patients may continue monotherapy with Omegaven® as an additional source of calories after the dextrose/protein portion of PN is discontinued

In the event that a patient who has been listed for a liver or liver/intestinal transplant has an organ become available, the participation in this protocol will not preclude them from receiving the transplant.

Disruption of Therapy

In event that Omegaven® cannot be administered (i.e. loss of central venous catheter access, fluid restrictions, need to administer an incompatible medication/blood product), the infusion of Omegaven® may be interrupted and resumed when the conflicting situation is resolved. Some potential interventions that can be used include:

Situation	Possible Solution
Loss of central venous access	Administer via peripheral route
Fluid restriction	Consult with pharmacy to concentrate PN, medications to allow for administration

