Generally, primary safety analyses will be based on time from baseline or 30 days after baseline until two months after patients first reached direct bilirubin levels $< 2\text{mg/dL}$. Baseline will be defined as information collected at the date that treatment starts for Omegaven[®] patients and on the date that patient reached bilirubin levels > 2 for soybean oil fat emulsion patients. Information on mortality and transplant will be collected during the whole treatment with Omegaven[®] and during the whole period for which we have data available in the Andorsky et al. dataset. Primary efficacy analysis will include time from baseline until the patient normalizes bilirubin (presents three consecutive direct bilirubin $\leq 2\text{ mg/dL}$ or a direct bilirubin $\leq 2\text{ mg/dL}$ and weaned from TPN). With exploratory purpose, we will also describe the curve of the several markers for the entire period that Andorsky et al. recorded data.

Outcome/Endpoints

1. Treatment safety

Our primary outcome for treatment safety will be based on patient's essential fatty acid profile. We will compare patients before treatment with Omegaven[®] started and after treatment started (one month after treatment started until treatment stopped) with respect to the frequency with which triene/tetraene ratio > 0.2 at any time. We will also compare the occurrence any event of of hypertriglyceridemia (serum triglyceride $> 400\text{mg/dL}$) between Omegaven[®] and soybean oil fat emulsions. Primary analyses for these and all other safety outcomes will be based on a follow-up time for Omegaven[®] and soybean oil fat emulsions starting 30 days after baseline, i.e., 30 days after treatment started for Omegaven[®] patients and 2 months after the first direct bilirubin level $< 2\text{ mg/dL}$ was recorded. We will also explore comparisons including the time from baseline until the end of follow-up period.

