Additional comparisons across treatment periods for subjects receiving Omegaven® will be aimed to assess occurrence of spontaneous bleeding (e.g., unexplained bruising, oozing from gums/incision sites), and maximum triene/tetraene ratio, minimum platelets, and maximum international normalized ratio (INR), trends in pre-albumin (age standardized levels). We will also explore trends in coagulopathies based on curves of platelets, prothrombin time (PT), partial thromboplastin time (PTT) over time, and INR. We will also describe the rate with which INR ratios were > 2 (number of days/follow-up time), as a marker of coagulopathies.

Additional comparisons between Omegaven® and soybean oil fat emulsion groups will be performed with regards to rate in which albumin is > 3 g/dL, maximum triglyceride level, rate of blood stream infections (number of positive blood cultures/follow-up-time under PN after baseline), rate of central venous catheter (CVC) infections (number of CVC infections/follow-up time and number of gram positive CVC infections/follow-up time), and occurrence of anaphylactic reactions after baseline.

Nutritional outcomes between Omegaven® and soybean oil fat emulsion groups that will be compared include changes in weight- and height-for-age Z-scores from baseline to 10% PN or cessation of PN..

We will describe trends over time for all outcomes associated with fatty acid profiles (including triene/tetraene ratios, triglycerides, total omega-6 fatty acids, total omega-3 fatty acids, total saturated, total monounsaturated, and total polysaturated fatty acids). Specific fatty acids such as arachidonic, palmoleic, palmitic, oleic, stearic, and linoleic fatty acids will also be evaluated and described. Also, for exploratory purposes, we will compare the trend in weight- and height-for-age Z-scores between both groups.

2. Omegaven®

3. The patient will complete treatment with Omegaven® in this study when he/she is completely off PN, develops a contraindication for further use, or the patient/family requests to be removed from the study.

f. Data Collection Methods, Assessments and Schedule

Omega-3 Fat Emulsion (Omegaven™)

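### The primary efficacy event includes a PN-weaning route in the endpoint section but not in the analysis section that feeds the survival analyses

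*Combined protocol and SAP*

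**What the plan says.** Two sections define the primary efficacy event.

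- **Section e, Definition of Primary and Secondary Outcomes/Endpoints.** "Primary efficacy analysis will include time from baseline until the patient normalizes bilirubin". A parenthesis then gives two routes: three direct bilirubin values in a row at or below 2 mg/dL, or one such value "and weaned from TPN".
- **Section 5c, Analysis of Efficacy of Omegaven®.** The outcome is time from baseline to normalisation, spelled out as the "first time point among three consecutive in which bilirubin is < 2 mg/dL". There is no weaning route. The Kaplan-Meier, log-rank and Cox analyses follow directly. Death or transplant before normalisation is given an infinite time. Nothing is said about a patient weaned after one or two normal values.

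Three other places bear on the point.

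- The study design text uses the same two routes for the earlier short-bowel control cohort, in a list that ends "and were weaned from PN died, or underwent a liver transplant". It uses them to close follow-up, 2 months after one of them is met. It does not call them the event.
- Duration of Therapy: "Patients will remain on Omegaven® until weaned from PN". Omegaven® alone may continue "as an additional source of calories after the dextrose/protein portion of PN is discontinued". The outcomes section says that a patient completes treatment "in this study when he/she is completely off PN".
- The laboratory schedule in 5f sets minimum testing. An inpatient off Omegaven® has one further full set. An outpatient is tested monthly until off Omegaven® with at least one direct bilirubin below 2 mg/dL.

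**The concern.** Treatment normally ends at weaning, and required blood tests can end soon afterwards. A child whose bilirubin normalises shortly before weaning may therefore have only one or two normal values on record. Under section e that child is a responder. Under 5c the child never reaches the event, and no rule is given for the follow-up time.

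The primary event would then depend on which section the analyst follows. In an open-label comparison with historical controls, that choice should be settled before the event data are analysed.

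**Working it through.** The documents give no event count, hazard ratio or power for this endpoint, so there is no figure to reproduce. Tables 4 and 5 concern adverse-event proportions and do not depend on the definition.

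**1. The two definitions side by side**

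| | Section e | Section 5c |
|---|---|---|
| Three-value route | direct bilirubin ≤2 | bilirubin <2, as printed |
| Weaning route | one value ≤2 and weaned | none |
| Event date | not stated | first of the three values |
| Weaned with one or two normal values | event | no event |

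**2. When does a weaned patient lack a third value?** Let s be the time from the first normal direct bilirubin to stopping Omegaven®. Assume that all later values stay normal, that only minimum tests are done, and that the weekly PN profile includes direct bilirubin. The last point is not stated, but the schedule is driven by direct bilirubin and no other listed test supplies it.

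- *Inpatient* (weekly, then one set after stopping): values = floor(s in weeks) + 1 + 1. If s is under 1 week, this is 0 + 1 + 1 = 2, one short. From 1 week on it is at least 3.
- *Outpatient* (monthly, no further draw if one value below 2 is already held): values = floor(s in months) + 1. Under 1 month gives 1. From 1 to under 2 months gives 2. At 2 months it is 3.
- *Outpatient, with one draw at or after stopping*: values = floor(s in months) + 1 + 1. Under 1 month gives 2. From 1 month on it is at least 3.

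**3. Does another rule supply the missing value?** Interpolation (5c, Missing Values) covers gaps of up to two visits within follow-up, not values after the last test. The deviation rule in 5b acts on scheduled cycles that were missed. Neither helps once required testing has ended.

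**4. Control side.** Data for the earlier cohort were abstracted at two-week intervals, and its follow-up runs 2 months past the qualifying date. That is room for about 8 weeks / 2 = 4 further records, if bilirubin was drawn. The documents do not say that it was, and Potential Study Limitations expects more missing data in the controls.

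**5. Illustration with assumed shares only.** Suppose a share w of normalisers reaches the event only by weaning and is censored there under 5c. With exponential times, the hazard ratio (Omegaven® to control) is multiplied by (1 − w_Omegaven) / (1 − w_control). Starting from a true ratio of 1:

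- 20% in both groups: 0.80 / 0.80 = 1.00
- 30% Omegaven®, 10% control: 0.70 / 0.90 = 0.78
- 10% Omegaven®, 30% control: 0.90 / 0.70 = 1.29

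A Cox simulation with 3,000 per arm gave 1.00, 0.78 and 1.23. The shift can go either way and vanishes when the shares are equal. The documents give no value for w in either group.

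**The case against.** The best defence is that 5c is shorthand. Section e carries the formal heading for endpoint definitions, and 5c may only be adding the event date that section e lacks. This is arguable. But 5c restates the outcome as a definition, and an analyst who programs from it gets no weaning event.

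The available text is also incomplete. The outcomes list passes from treatment safety to a bare second item and then to completion of treatment, so an efficacy item may be missing. For that reason the claim is limited to visible text.

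Several provisions make a missing third value less likely: monotherapy after PN, at least 2 months of follow-up after Omegaven® (no test is named), the footnote that the schedule is a minimum, and the control provisions in step 4 of the working. All of these stand. They reduce the frequency but do not settle the definition. The analysis is also described as preliminary, and group sizes are not based on power.

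A reader might infer that the study design text is a further event definition in conflict with 5c. It is not. It sets the end of control follow-up and fits section e, but section e alone carries the conflict. A reader might also treat < against ≤ as a second substantive error. It matters only for values of exactly 2.0 and may come from text extraction.

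**Conclusion.** The conflict between section e and 5c is real, and it concerns the primary efficacy event. With minimum testing, the patients exposed are those who stop Omegaven® within 1 week of the first normal value as inpatients, or within 1 to 2 months as outpatients. These windows rest on the assumptions in step 2 of the working.

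A reader might go further and infer that the hazard ratio is biased for or against Omegaven®, or that many responders are lost. The documents support neither. They give no distribution of the time from normal bilirubin to stopping, and the hazard ratios shown rest on invented shares. Confidence is high that the wording conflicts. The effect on the result is unknown. The point should be corrected, and the correction is inexpensive.

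**What to change.** In 5c, replace the event definition with the two routes of section e, using direct bilirubin and one threshold, ≤2 mg/dL. Then:

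- **Event date.** Use the same rule for both routes: the first value of the unbroken run of values ≤2 mg/dL that either reaches three values or is still unbroken at weaning. For example, with normal values at months 0 and 1 and weaning at month 1.5, the event is dated at month 0 whether or not a third normal value is drawn. Dating the weaning route at weaning would put the event at 1.5 without that draw and at 0 with it.
- **Weaning.** State whether a patient on Omegaven® monotherapy counts as weaned for this endpoint. Also state whether a first value ≤2 mg/dL recorded after weaning meets the weaning route, since the run rule alone does not cover it.
- **Groups.** Apply the rule identically to the Omegaven® group and both control cohorts.
- **Sensitivity analysis.** Report the three-consecutive-values-only version.

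Treatment, the laboratory schedule and the safety windows stay as they are. Patients already at or below 2 mg/dL at baseline are a separate matter.

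**Cost.** A revised paragraph, the matching derivation and one extra analysis. A PN cessation date is already needed to close follow-up in the earlier control cohort and for the growth comparison, which runs "from baseline to 10% PN or cessation of PN". The plan does not say that this date is held for the contemporary controls, so up to 50 dates may need abstracting. The main drawback is that the weaning route can rest on a single value. The sensitivity analysis and the planned description of bilirubin rebounds would show how much that matters.
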